**16. Economic Burden to Subjects**

Describe any costs that subjects may be responsible for because of participation in the research study (for example, co-pays; paying for treatment, therapies, or other interventions, or the delivery of these) and how you will inform participants of these costs prior to their enrollment in this study.

N/A

**17. Compensation to Participants**

Describe any compensation provided to participants, for example, for time inconvenience, discomfort, travel, or in the event of research related injury. If applicable, describe how you will inform participants of this prior to their enrollment in the study, including if payment will be prorated if the subject withdraws early from the study.

NOTE: payment may not be withheld as an incentive for participants to complete any portion of the study.

Participants will receive a total of \$70 in the study for their participation. They will be issued:

- One \$20 Target e-gift card after completion of the first (baseline) survey and return of the worn physical activity monitor;
- One \$20 Target e-gift card after completion of the second (3 months post-baseline) survey and return of the worn physical activity monitor;
- One \$30 Target e-gift card after completion of the third (6 months post-baseline) survey, return of the worn physical activity monitor, and completion of the final survey (when the participant's baby is 12 months old).

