**Implementation evaluation measures.** Process measures and key stakeholder interviews will be used to assess the Reach, Effectiveness, Adoption, Implementation, and Maintenance components of the RE-AIM framework. *Reach* of the intervention will be evaluated using the participation rate among contacted eligible participants and comparison of characteristics available in the EHR between participants and eligible non-participants. *Effectiveness* will be measured through the results of the randomized controlled trial, by examining the data for a dose-response association between intervention engagement/adherence (number of exercise videos viewed), PA, and depressive symptoms, and through participant satisfaction with the intervention. Satisfaction will be assessed as part of the T1 online surveys. *Adoption* will be assessed by calculating personnel costs associated with the intervention (e.g. clinic referral staff). Additionally, key stakeholder interviews with clinicians and clinical leaders will address identified avenues for *adoption* of MomZing and barriers to *implementation* and *maintenance* within clinical practice at KPNC. The standard criteria for generating a RE-AIM public health impact score will be followed.

- The duration of an individual subject's participation in the study.

For the patient participants, participation will begin between 2 and 6 months postpartum (baseline), depending when they are recruited, and will conclude after the women complete the final survey when their child is 12 months old.

For the clinicians, participation is complete after the one-time interview to identify barriers and addressing implementation and evaluate potential adoption of MomZing.

- The duration anticipated to enroll all study subjects.

The anticipated duration to enroll all study subjects will be from 08/01/2020-03/31/2022.

		Year 1		Year 2		Year 3	
IRB approval		M					
MomZing development/final product		D					D
Clinic implementation workflow/protocol		D					D
Participant recruitment						M	
Data collection							M
Stakeholder interviews		M					M
Data analysis							M
MomZing effectiveness manuscript							D
Implementation findings report							D

M=milestone, D=deliverable

- The estimated date for the investigators to complete this study (complete primary analyses)  

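### The only payment for the 6-month assessment also requires the infant 12-month survey, which conflicts in effect with the no-withholding note in the same section

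*Combined protocol and SAP*

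**What the plan says.** Section 17 lists three gift cards totalling $70. The $20 baseline card depends on the baseline survey and return of the monitor. The T1 card, also $20, has the same form: "Target e-gift card after completion of the second (3 months post-baseline) survey and return of the worn physical activity monitor". The third card, $30, is issued after "completion of the third (6 months post-baseline) survey, return of the worn physical activity monitor, and completion of the final survey". The final survey is taken "when the participant's baby is 12 months old".

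The instruction text of the same section carries a note that "payment may not be withheld as an incentive for participants to complete any portion of the study". It also asks the investigator to explain how participants will be told about payment, "including if payment will be prorated if the subject withdraws early from the study". The answer does not mention proration.

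On timing, Section 9.a (Description) starts participation at 2 to 6 months postpartum and says that it "will conclude after the women complete the final survey when their child is 12 months old". Section 4 (Study Design) places T2 six months after baseline and adds that the final survey may fall at T2, depending on the infant's age at enrolment.

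On the role of the data, the Statistical Analysis text in Section 9.b puts minutes of moderate/vigorous activity and the PHQ-8 score at each time point in the primary analyses. The 12-month survey measures child development, which Section 2 lists under Exploratory Aim 1.

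**The concern.** The first two cards reward one assessment each. The third bundles T2 with a later and separate task. As written, a woman who returns the T2 survey and monitor has earned nothing until she also completes the infant survey, and if she never does, her T2 work goes unpaid. A woman who withdraws, or is withdrawn, between T2 and the 12-month survey is in the same position, because proration is not addressed.

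Two things are at stake. The first is consistency with the section's own note: holding back payment for finished work until a further part of the study is complete has the effect that the note rules out. The second is priority. T2 supplies accelerometer and PHQ-8 data for the primary analyses, while the 12-month survey is exploratory. It would be unfortunate if the payment terms weakened the return of the former in order to support the latter.

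**Working it through.** **1. Payment terms side by side (Section 17)**

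| Card | Amount | Conditions |
|---|---|---|
| Baseline | $20 | baseline survey + monitor |
| T1 | $20 | T1 survey + monitor |
| Third | $30 | T2 survey + monitor + infant 12-month survey |

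Total: 20 + 20 + 30 = $70, as stated. Only the third card depends on a task outside its own assessment.

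**2. Length of the wait**

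Wait after T2 = 12 − (infant age at enrolment + 6) months.

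| Infant age at enrolment (months) | 2 | 3 | 4 | 5 | 6 |
|---|---|---|---|---|---|
| Infant age at T2 (months) | 8 | 9 | 10 | 11 | 12 |
| Wait (months) | 4 | 3 | 2 | 1 | 0 |

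For infants enrolled at about 6 months the wait disappears, as Section 4 anticipates. The extra condition on payment remains for everyone.

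**3. The plan's own power figures (Section 9.b)**

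Inputs: 100 women per arm, up to 16% loss, hence 84 per arm; two-sided alpha .05; power .80.

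- Detectable difference: (1.960 + 0.842) × √(2/84) = 0.432 SD (0.435 with the t distribution). The plan states .43.
- Power for 43% against 23% meeting activity guidelines, 84 per arm, pooled variance, no continuity correction: .79. The plan states .80.

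Both figures reproduce. They use up the whole 16% allowance, so any further loss would lower power below plan.

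**4. What extra T2 loss would do (illustration only)**

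Assumption, not in the documents: 5 or 10 further women per arm miss T2 but have T1 data.

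*Contrast using T2 alone:*

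| n per arm | Detectable difference, 2.802 × √(2/n) | Power for 0.432 SD | Power, 43% v 23% | Rise in SE, √(84/n) |
|---|---|---|---|---|
| 84 | 0.432 SD | .80 | .79 | – |
| 79 | 0.446 SD | .78 | .77 | 3.1% |
| 74 | 0.461 SD | .75 | .74 | 6.5% |

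*Pooled arm effect in the GEE model.* A woman with T1 but not T2 stays in the analysis. Take an effect common to both follow-up times, equal variances and an exchangeable correlation r between T1 and T2. A woman with both visits then contributes information 2/(1 + r), and a woman with T1 only contributes 1. With m of 84 women per arm having T1 only, information relative to complete data is

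(84 − m)/84 + m(1 + r)/(2 × 84).

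For m = 10:

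- r = 0.3: 0.881 + 0.077 = 0.958, so the SE rises by 1/√0.958 − 1 = 2.2%.
- r = 0.7: 0.881 + 0.101 = 0.982, so the SE rises by 0.9%.

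For m = 5 the rise is 1.1% and 0.4% respectively. The correlations are assumed.

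**The case against.** The strongest reply has five parts.

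- **The note is institutional template text**, and the protocol nowhere says that payment is held back in order to induce completion. Read with full literalness, the note might also catch the baseline and T1 cards, which are held until both a survey and a monitor are in. This stands as a limit: the conflict lies in the effect of the terms, not in any declared intent. But bundling a survey with its own monitor is different from making one completed assessment wait on a later, separate one.
- **The delay varies.** A reader might infer that every woman waits four months. Section 4 does not support that; four months applies only to infants enrolled at 2 months.
- **The retention effect is unknown.** A reader might infer that the trial loses power or is biased. The documents give no figure for how payment timing affects return. The third card is the largest, which may partly offset the delay, and a T2 card within the same total would be smaller than $30. Terms are identical in both arms, so nothing here points to bias.
- **Other retention measures exist.** The research assistant sends reminders (Section 6), and prepaid return envelopes are supplied (Section 9.a).
- **The consent form is not available for this review**, so what women are told about payment on early withdrawal cannot be checked.

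These points limit the size of the concern. They do not remove the mismatch within Section 17.

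**Conclusion.** The point holds as a matter of text: completed T2 work is paid only if the infant survey follows, against the section's note and unlike the other two cards. The wait is about 0 to 4 months, and forfeiture is possible for any woman who completes T2 but not the final survey.

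The statistical consequence is unquantified and probably small. No power or sample-size figure in the plan is shown to be wrong. The losses in power above rest on an assumed 5 to 10 extra women lost per arm and apply only to a T2-only contrast. For the pooled GEE estimate, 10 such women per arm would raise the standard error by about 1 to 2%, given correlations of 0.3 to 0.7 and a common effect over time. This is a cheap improvement, not a threat to the trial's conclusions.

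**What to change.** In Section 17, and in the matching consent wording, split the third card. Issue one card when the 6-month survey is complete and the monitor is back (for example $20, matching T1), and a separate card for the 12-month survey (for example $10). The total stays at 20 + 20 + 20 + 10 = $70. Add a sentence answering the proration question: women who withdraw or are withdrawn keep payment for the assessments they have completed.

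The cost is one more e-gift card transaction per woman and a small consent revision. The split may slightly lower response to the 12-month survey, which is exploratory. It also makes the T2 card smaller than $30, in exchange for paying it promptly and without a further condition.

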#### 18. Resources Available

Describe any special resources or expertise required to conduct the study.

N/A

#### 19. Principal Investigator

- a. Has the Principal Investigator (PI) previously been approved as PI for a study within KPNC?  Yes  No
- b. Has the PI been audited/assessed within the past three years?  Yes  No  
If Yes, check all that apply and provide the outcome/findings:  
 FDA  RQCC  CTP  CCRU  
Outcome/Findings: Click or tap here to enter text.
- c. Is the PI currently under a Corrective And Preventative Action (CAPA) plan?  
 Yes  No  
If Yes, provide a brief description: Click or tap here to enter text.

## 21. Drugs or Devices

NOTE: see the ICH-GCP guidance for a summary of investigator and sponsor responsibilities in clinical trials.

List all drugs and devices used in the research and the purpose of their use, and their regulatory approval status.

N/A

### a. Drug Studies

If the research involves drugs and is investigator-initiated, indicate whether there is any possibility that the results will be reported to FDA (e.g. as part of a new drug application [NDA]).

N/A

If the drug is investigational (has an IND), confirm that you will comply with all applicable FDA requirements for investigators.

N/A

Confirm that you will follow applicable KP pharmacy policies and procedures.

N/A

Describe your plan for drug storage, handling, and accountability, including distribution, return, and destruction of the drug(s).

N/A

b. Device Studies:

If this is a device study and you think the device is Non-Significant Risk, include justification here or upload it as a separate document along with any available device information (instructions for use, etc.).

N/A

If the research involves devices and is investigator-initiated, indicate whether there is any possibility that the results will be reported to FDA (e.g. as part of a premarket approval application [PMA]).

N/A

If the device has an IDE or a claim of abbreviated IDE (Non-Significant Risk device), confirm that you will comply with all applicable FDA requirements for investigators.

N/A

Describe the device, the manufacturing process, and the device labeling, including safety instructions or warnings. If available, this may be addressed in separately uploaded device information (such as instructions for use).

N/A

Describe device storage, handling, and accountability, including how access to the device will be limited to appropriate personnel and how you will ensure the device will be used only for appropriate study subjects.

N/A

**22. Multi-Site Research**

- a. If this is a multi-site study and you are the lead investigator or this site will be the coordinating center for any activity, describe the processes to ensure communication among sites, such as:

- All sites have the most current version of the protocol, consent document, and HIPAA authorization.

N/A

- All required approvals have been obtained at each site (including approval by the site's IRB of record).

N/A

- All modifications have been communicated to sites, and approved (including approval by the site's IRB of record) before the modification is implemented.

N/A

- All engaged participating sites will safeguard data as required by local information security policies.

N/A

- All local site investigators conduct the study appropriately.

N/A

- b. Describe the method for communicating to engaged participating sites the following:

- Problems.

N/A

- Interim results.

N/A

- The closure of a study.

N/A

- c. Describe any special resources or expertise required to conduct the study.

N/A

### 23. Community-Based Participatory Research

Describe involvement of the community in the design and conduct of the research.

N/A

Describe your plan for ensuring that community research partners are appropriately trained in human subjects' protection.

N/A

NOTE: "Community-based Participatory Research" is a collaborative approach to research that equitably involves all partners in the research process and recognizes the unique strengths that each brings. Community-based Participatory Research begins with a research topic of importance to the community, has the aim of combining knowledge with action and achieving social change to improve health outcomes and eliminate health disparities.
